8.2 SAFETY ASSESSMENTS

N/A

8.3 ADVERSE EVENTS AND SERIOUS ADVERSE EVENTS

8.3.1 DEFINITION OF ADVERSE EVENTS

This protocol uses the definition of adverse event from 21 CFR 312.32 (a): any untoward medical occurrence associated with the use of an intervention in humans, ***whether or not considered intervention-related.***

8.3.2 DEFINITION OF SERIOUS ADVERSE EVENTS

Should an event be reported to the research team, it will be referred to the IRB for classification as to the severity of the event.

8.3.3 CLASSIFICATION OF AN ADVERSE EVENT

8.3.3.1 SEVERITY OF EVENT

This study will evaluate a group-level intervention of an organization’s opioid-related policies and procedures delivered by union health funds, and disseminated to their membership. We will not collect individual identifiers, thus we will likely not have data on Adverse Events or Serious Adverse Events related to the intervention.

8.3.3.2 RELATIONSHIP TO STUDY INTERVENTION/EXPERIMENTAL MANIPULATION

In the event that we learn of an adverse event, we will adhere to the following reporting timeframes:

- Adverse Events will be reported to the NIDA Program Officer (PO) as part of the annual progress report. Although we will not know the identity of the individual involved, in the report we will describe the event, when it occurred, and the outcome (if known).

- Serious/Unanticipated Adverse Events will be reported to the NIDA PO within 24 hours, with a follow-up on the status of the event within 72 hours later, although it is unlikely an individual will experience a SAE as a result of participation in the study.
- We will also report all AEs to the IRB within 10 working days of when we become aware of the event, as required by the IRB.
- It will likely be difficult to know if the event is related to the intervention, however the event will be reported if the research team is notified.

8.3.3.3 EXPECTEDNESS

It is unlikely that an Adverse Event will be related to the intervention, as the implementation of the intervention is at the discretion of the union health fund and likely subject to the Trustee Board Approval. However, if an event does occur, it will be reported.

8.3.4 TIME PERIOD AND FREQUENCY FOR EVENT ASSESSMENT AND FOLLOW-UP

- Serious/Unanticipated Adverse Events will be reported to the NIDA PO within 24 hours, with a follow-up on the status of the event within 72 hours later, although it is unlikely an individual will experience a SAE as a result of participation in the study.
- We will also report all AEs to the IRB within 10 working days of when we become aware of the event, as required by the IRB.

8.3.5 ADVERSE EVENT REPORTING

Serious/Unanticipated Adverse Events will be reported to the NIDA PO.

We will also report all AEs to the IRB.

8.3.6 SERIOUS ADVERSE EVENT REPORTING

Serious/Unanticipated Adverse Events will be reported to the NIDA PO.

We will also report all AEs to the IRB.

8.3.7 REPORTING EVENTS TO PARTICIPANTS

N/A

8.3.8 EVENTS OF SPECIAL INTEREST

N/A

8.3.9 REPORTING OF PREGNANCY

N/A

8.4 UNANTICIPATED PROBLEMS

8.4.1 DEFINITION OF UNANTICIPATED PROBLEMS

This protocol uses the definition of Unanticipated Problems as defined by the Office for Human Research Protections (OHRP). OHRP considers unanticipated problems involving risks to participants or others to include, in general, any incident, experience, or outcome that meets all of the following criteria:

- Unexpected in terms of nature, severity, or frequency given (a) the research procedures that are described in the protocol-related documents, such as the Institutional Review Board (IRB)-approved research protocol and informed consent document; and (b) the characteristics of the participant population being studied;
- Related or possibly related to participation in the research (“possibly related” means there is a reasonable possibility that the incident, experience, or outcome may have been caused by the procedures involved in the research); and
- Suggests that the research places participants or others at a greater risk of harm (including physical, psychological, economic, or social harm) than was previously known or recognized.]

8.4.2 UNANTICIPATED PROBLEMS REPORTING

The investigator will report unanticipated problems (UPs) to the reviewing Institutional Review Board (IRB) and to the Data Coordinating Center (DCC)/lead principal investigator (PI). The UP report will include the following information:

- Protocol identifying information: protocol title and number, PI’s name, and the IRB project number

- A detailed description of the event, incident, experience, or outcome
- An explanation of the basis for determining that the event, incident, experience, or outcome represents an UP
- A description of any changes to the protocol or other corrective actions that have been taken or are proposed in response to the UP

To satisfy the requirement for prompt reporting, UPs will be reported using the following timeline:

- UPs that are serious adverse events (SAEs) will be reported to the IRB and to the DCC/study sponsor/funding agency within 24 hours of the investigator becoming aware of the event
- Any other UP will be reported to the IRB and to the DCC/study sponsor/funding agency within 7 days of the investigator becoming aware of the problem
- All UPs should be reported to appropriate institutional officials (as required by an institution's written reporting procedures), the supporting agency head (or designee), and the Office for Human Research Protections (OHRP) within 30 days of the IRB's receipt of the report of the problem from the investigator

8.4.3 REPORTING UNANTICIPATED PROBLEMS TO PARTICIPANTS

N/A

9 STATISTICAL CONSIDERATIONS

9.1 STATISTICAL HYPOTHESES

This is a feasibility trial to evaluate the ability to recruit and enroll health funds, collect endpoint data for primary and secondary outcome measures, and to collect process measures related to implementation of the intervention with three health funds. There is no formal hypothesis testing in this trial although we will calculate descriptive statistics at baseline and follow-up (6-months) to show change over time. The data will be used to compute statistical power for a future R01 if the current study is successful.

- Primary Endpoint(s):
 - a) We will calculate the Proportion of workers with opioid misuse, opioid use disorder and opioid overdose using administrative data. We will assess change of opioid misuse and opioid use disorder at 6 months following delivery of the intervention
 - b) We will calculate the proportion of workers with opioid misuse from worker surveys. We will assess change in opioid misuse at 6 months following delivery of the intervention.

- Secondary Endpoint(s):
 - a) We will calculate the proportion of workers with lost time using worker surveys. We will assess change in reported lost time at 6 months following delivery of the intervention.
 - b) We will calculate the proportion of workers reporting willingness to seek help for opioid abuse using worker surveys. We will assess change in reported willingness to seek help at 6 months following delivery of the intervention.

9.2 SAMPLE SIZE DETERMINATION

There were no power sample calculations for this study as it is a feasibility pilot study. The data generated from this study will inform the power calculations for a future R01, if the pilot study is successful.

We estimated the number of participants needed for surveys from the sample sizes needed to document change over time for similar behavior outcomes from past studies. The data will be collected at two points in time (baseline and 6-months after start of the intervention). We will collect cross-sectional data, and calculate the group-level change pre-post intervention. We will collect 300 surveys for each participating health fund at baseline and at 6-months post-intervention, and at 12-months time permitting. This will be a minimum of 1800 surveys, or 2700 surveys time permitting.

We estimated the number of participants for the administrative data from the membership sizes of union health funds from past studies. In past studies, union health fund members have covered 10,200 members. We estimate we will collect administrative data for 10,200 members for each of three health funds (total of 30,600) members.

9.3 POPULATIONS FOR ANALYSES

We will calculate descriptive statistics for the full population of the administrative data. The data will include active and retired members from the benefits-eligible group of the period May 2019-May 2022. We will include any member who was continuously benefits-eligible but censor them after they drop eligibility or don't self-pay to continue coverage. All retired members who self-pay will also be included in the analyses.

We will calculate descriptive statistics for those members who complete the worker survey. We will compare the demographics (age, gender, race) of those who completed the survey to the union

membership to see if the two groups (surveyed versus union members) have similar characteristics. This will help assess the feasibility of the survey recruitment methods to obtain a representative sample.

9.4 STATISTICAL ANALYSES

9.4.1 GENERAL APPROACH

Outcome data is derived from the administrative claims and worker surveys.

Administrative claims will be collected over two periods (06/01/2019-05/31/22) and (06/01/2022-05/31/2023). All three outcomes of interest are primary outcomes. The analysis will examine the group level change of the outcome, adjusting for length of time in each period, to show a reduction in impaired health or behaviors that may be due to implementation of the intervention.

Worker surveys will be collected by member worker surveys from each health fund at two points in time. The baseline, before implementation of the intervention, and at 6-months after start of implementation. All members will be invited to complete a survey. The desired sample is 300 surveys per health fund at each time point. The outcomes are composed of one or more items in the surveys. Group level statistics will be computed as the proportion of members with a positive response to each outcome. The change in proportion by time point may be due to implementation of the intervention.

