3 OBJECTIVES AND ENDPOINTS

The objective of this trial is to evaluate the feasibility of implementing the workplace opioid guidelines in union health funds of the construction trades and measure the implementation and effectiveness of changes made to the union health fund policies, programs, and benefits made in response to using the workplace guidelines. We will assess implementation using process measures recorded over a 6-month period of time using the REAIM framework. We will assess effectiveness by measuring changes in the administrative claims and from worker surveys collected from members.

The primary outcomes will show a change in a) the proportion of workers with opioid misuse, opioid use disorder and opioid overdose collected from administrative data over a 4 year period (3-years prior to the intervention, and one-year of the intervention implementation) and b) the proportion of workers with opioid misuse measured from worker surveys from each of the union health funds over a 6-month period after start of implementation of the intervention.

The secondary outcomes will show a change in a) the proportion of workers with lost time measures and b) the proportion of workers willing to seek help measured from worker surveys from each of the union health funds, and collected over a 6-month period after start of the implementation of the intervention.

The feasibility trial will be deemed successful if the study successfully recruits three union health funds, and collects measures to assess the implementation of the intervention and effectiveness of health and behaviors during the trial period. This is not a randomized trial, nor is the study powered to expect statistical changes in the outcome measures. The benefit for conducting the feasibility trial is to test all procedures in the specific population to guide plans for a future randomized trial.

OBJECTIVES	ENDPOINTS	JUSTIFICATION FOR ENDPOINTS
Primary		

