9.4.2 ANALYSIS OF THE PRIMARY ENDPOINT(S)

- a) Administrative Claims
 - a. Outcome variables of interest
 - i. Opioid misuse- “Overlapping Rx” OR “Multiple Rx on same day, different provider”
 - ii. Chronic opioid use- more than 60 days supply in a 90 day window
 - iii. Opioid use disorder- ICD-10 T40* (Poisoning by, adverse effect of and underdosing of narcotics and psychodysleptics) &/Or ICD-10 F11* (opioid related disorders) &/or prescribed MAT (Drug name contained “methadone” or “buprenorphine”; picks up buprenorphine, suboxone, zubsolv, naltrexone, methadone, narcan, and vivitrol)
 - b. Compute statistics for baseline period (06/01/2019-05/31/2022) and follow-up (06/01/2022-05/31-2023)

- i. Categorical data will be presented as N (%), continuous data as median (25th, 75th %tile)
- c. Run comparisons between baseline and follow-up time points
 - i. Comparisons involving two categorical variables will be made using Fisher's exact test
 - ii. Comparisons involving a continuous variable and a categorical variable will be made using Wilcoxon Rank Sum test or Kruskal Wallis test

b) Worker Survey

- a. Outcome variable of interest
 - i. Opioid misuse- Participant responded yes to one of the following two questions:
 - 1. Did you use the pain medication more than prescribed, or for a longer period than prescribed? [pnmed_longer]x
 - 2. Have you used prescription pain medications that were prescribed to someone else? [pnmed_othersrx]x
 - b. Compute the change at 6 months post-intervention (change of opioid misusep) of group-level data collected from groups of health

All endpoints are independent outcomes.

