9.4.7 SUB-GROUP ANALYSES

If there is adequate data collected for more than one health fund, we will stratify the data by health fund group to assess the similarity and differences in the demographics of each of the health fund characteristics (age, gender, race) and by the primary and secondary endpoints. We will use these results to help inform future decisions toward conducting an R01 trial.

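### Section 9.4.2 orders significance tests on three unranked primary claims outcomes, although Section 9.1 says the trial has no formal hypothesis testing

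*Combined protocol and SAP*

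**What the plan says.** Section 3 ties success to recruiting three health funds and collecting the measures, and adds: "This is not a randomized trial, nor is the study powered to expect statistical changes in the outcome measures". Section 9.1 is explicit: "There is no formal hypothesis testing in this trial although we will calculate descriptive statistics at baseline and follow-up (6-months) to show change over time".

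Section 9.4.1 says of the claims data: "All three outcomes of interest are primary outcomes". It frames the claims analysis as showing a reduction that the intervention may explain, and it promises adjustment for the length of each period.

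Section 9.4.2 a lists three claims outcomes: misuse ("Overlapping Rx” OR “Multiple Rx on same day, different provider"), chronic use (over 60 days' supply within 90 days) and opioid use disorder (OUD). It then calls for comparisons between the periods: "Comparisons involving two categorical variables will be made using Fisher's exact test", with Wilcoxon or Kruskal-Wallis tests where a variable is continuous. For the survey misuse endpoint, Section 9.4.2 b asks only that the change be computed.

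Section 9.4.2 closes with "All endpoints are independent outcomes", and Section 9.4.3 closes with the same sentence. No section gives a significance level, an order among the outcomes, a multiplicity statement or a label marking the tests as descriptive. The Protocol Amendment History reports no changes that would resolve this.

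**The concern.** An analyst cannot follow both Section 9.1 and Section 9.4.2 a. Following the latter produces at least three p-values on outcomes called primary, in an analysis whose stated aim is to show a reduction. Nothing tells a reader what weight to give them, or what to conclude if they disagree.

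The results will travel. Section 10.1.10 commits to ClinicalTrials.gov posting and attempts at journal publication, Section 9.2 says the data will inform power calculations for a later trial, and Section 2.3.2 says the observed changes will help determine the guidelines' effectiveness. In each place, one p-value below 0.05 on a primary outcome could be taken as an effect that the study was not designed to test.

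The sentence on independent outcomes adds to the risk, because claims misuse and chronic use come from the same opioid fills. One shift in prescribing could move both and be read as two separate confirmations.

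**Working it through.** **The plan's own figure.** The documents state no error rate, so there is none to reproduce.

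**Inputs.** Three tests (Sections 9.4.1 and 9.4.2 a). Significance level: not stated; two-sided 0.05 assumed. Correlation between test statistics: not stated; 0 to 0.9 shown.

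**Three independent tests.** Chance of at least one false-positive = 1 − (1 − α)³ = 1 − 0.95³ = 0.1426, which is 0.1426 / 0.05 = 2.85 times one test. The ratio changes little with α: 2.97 at 0.01 and 2.71 at 0.10.

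**Three correlated tests.** One million simulated sets of three equally correlated normal statistics, each rejected beyond the two-sided 0.05 limit:

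| Correlation | At least one false-positive | Ratio to 0.05 |
|---|---|---|
| 0 | 14.3% | 2.85 |
| 0.5 | 12.5% | 2.5 |
| 0.7 | 11.0% | 2.2 |
| 0.8 | 9.8% | 2.0 |
| 0.9 | 8.4% | 1.7 |

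**Direction.** These figures count increases as well as reductions. For false reductions alone, three independent tests give 1 − 0.975³ = 7.3%.

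**Conservatism of Fisher's test.** Its actual size was simulated at 10,200 and 30,600 members per period, the counts in Section 9.2. With assumed outcome proportions of 0.5% to 3%, three independent tests give about 12% to 14%. At 0.1% they give about 8% to 11%.

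**Is each test valid on its own?** Baseline runs from 06/01/2019 to 05/31/2022 (three years) and follow-up from 06/01/2022 to 05/31/2023 (one year). Fisher's test on counts and percentages makes no adjustment for this. Take an assumed constant annual rate of 0.2% and no true change:

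- ever-positive over three years: 1 − exp(−0.006) = 0.60%
- ever-positive over one year: 1 − exp(−0.002) = 0.20%

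With 10,200 members per period, a two-proportion comparison of these rejects about 99.5% of the time, and more often at higher rates. An unpaired test also ignores that many members may contribute to both periods. The table therefore holds only if these faults are removed.

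**Shared source of two outcomes.** The data management appendix (listed in Section 10.2) defines overlap as a fill dated before the previous fill's supply runs out. It defines chronic use from days' supply summed in 90-day cycles. Both use the same workers' fill dates and days' supply.

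**Which three outcomes.** The Protocol Summary and Sections 3 and 9.1 name misuse, OUD and overdose. Section 9.4.2 a lists misuse, chronic use and OUD; overdose is not separate there, although poisoning codes (T40) fall within its OUD definition.

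**The case against.** The strongest reply is that this is a feasibility study. Success in Section 3 rests on recruitment and data collection, no stopping or go/no-go rule uses a p-value, and family-wise control protects a confirmatory claim that nobody plans to make. This stands, and it limits the consequence. It does not remove the contradiction, because Section 9.4.2 still orders the tests and Section 9.4.1 still aims at a reduction.

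Several stronger readings are tempting but unsupported:

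- A reader might infer that the survey misuse endpoint is a fourth test. Section 9.4.2 b plans only a computed change.
- A reader might infer a further set of tests within each fund. Section 9.4.7 says "we will stratify the data by health fund group", but only if data are adequate, and it names no test.
- A reader might take the sentence on independent outcomes as a false claim of statistical independence. It may mean only that each endpoint is reported on its own. The fair criticism is that it is ambiguous. Positive correlation also lowers the family-wise rate, so dependence does not add to the multiplicity figure.

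It can also be said that one sentence calling the tests descriptive would reconcile the sections. That is true of the wording, but it would keep tests that ignore the unequal periods and repeated members.

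**Conclusion.** The concern holds in a limited form. Sections 9.1 and 9.4.2 a contradict each other, and the resulting p-values on unranked primary outcomes have no stated interpretation. At an assumed two-sided 0.05, with each test valid, the chance of at least one false-positive among three is about 8% to 14% for correlations from 0.9 down to 0, somewhat less for rare outcomes under Fisher's test. It would be wrong to infer that this is the plan's actual false-positive risk: unadjusted comparison of three years with one year could reject far more often. It would also be wrong to infer that the trial's conclusion is at stake, since feasibility alone decides success. What is at stake is over-reading a p-value in reports or in planning the next trial. Which three claims outcomes are primary is a separate inconsistency that must be settled alongside.

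**What to change.** 1. **Section 9.4.2 a:** replace the Fisher, Wilcoxon and Kruskal-Wallis comparisons with the estimated change and a 95% confidence interval for each endpoint. Adjust for period length, as Section 9.4.1 already requires, for example with rates per person-year of eligibility. Allow for members in both periods, for example with member-level robust standard errors. Label the results descriptive and unadjusted for multiplicity, with no significance claims; the label matters because an interval can be read against zero just as a p-value can.
2. **Section 9.4.1:** state the purpose as *to estimate the change* rather than to show a reduction.
3. **Sections 9.4.2 and 9.4.3:** replace the sentence on independent outcomes with *Endpoints are reported separately.* In 9.4.2 add that claims misuse and chronic use are derived from the same opioid fills and are not independent evidence.
4. **Protocol Summary and Sections 3, 9.1 and 9.4.2:** name the same three primary claims outcomes, resolving overdose against chronic use.

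This takes a few lines of text and no new data. The downside is that no p-values can be quoted for the claims outcomes. Interval estimates suit the planning of the next trial better.
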